9. CLINICAL SITE EFFECTS

Several procedures have been incorporated into the study design (i.e., procedure manual, training and certification programs, protocol violation monitoring, blinding) to reduce center effects; however, these effects should not be ignored for this trial. The distribution of center demographics will be examined. Means, standard deviations, proportions and 95% confidence intervals will be presented. Center and center*treatment interaction terms will be included in a secondary analysis of the primary outcome as a random effect.

10. EFFICACY ANALYSIS

10.1 Primary Outcome Variable Analysis

10.1.1 Statistical Hypothesis

The set of statistical hypotheses is:

$$H_0: b \text{ coefficient}_{\text{treatment}} = 0 \quad \text{versus} \quad H_A: b \text{ coefficient}_{\text{treatment}} \neq 0$$

where $b \text{ coefficient}_{\text{treatment}}$ is the regression coefficient for the variable 'treatment'.

10.1.2 Primary Efficacy Analysis at the End of the Trial

The primary outcome analysis of the 90-day mRS will use a stratified dichotomy methodology for assessing improvement as defined in the Primary Outcome section above. Outcome differences will be analyzed under the intention-to-treat principle, therefore all randomized subjects will be included in the primary analysis sample. To assess efficacy, the treatment groups will be compared with respect to the proportion with favorable outcome 90 days post randomization after controlling for the variables included in the randomization scheme. The primary statistical analysis will develop a generalized linear model using the PROC GENMOD procedure in SAS® v9 with treatment group as the factor of interest and baseline NIHSS strata (3-7, 8-14, 15-22) and thrombolysis use (Yes/No; includes both IV and IA therapies) as covariates. A Wald

[figure not shown]
chi-square test will be performed to compare the treatment group proportions using a two-tailed significance level of 0.05. Adjusted relative risks will be reported with two-sided 95% confidence intervals. Additional analyses will identify potential confounding (prognostic) variables to be used as covariates in subsequent secondary analyses of the primary outcome. Specific covariates include age, gender, race, ethnicity, admission blood glucose, previous stroke, lacunar subtype, and time between stroke onset and treatment. If statistically significant differences are evident, then post-hoc analyses will be conducted to determine if differences had an effect on the conclusions from the pre-specified primary analysis.

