3. OUTCOME VARIABLES

3.1 Primary Efficacy Outcome

The primary efficacy outcome is the severity adjusted 90-day mRS. Favorable outcome is defined using a responder analysis method.^{1,2} This method is proposed for the SHINE trial to provide a more sensitive measure of clinical effect. The responder analysis dichotomizes mRS scores as “favorable” versus “not favorable” based on the baseline NIHSS measured at randomization. “Favorable” outcome is defined as an mRS score of 0 in patients with baseline NIHSS of 3-7, mRS of 0-1 in patients with baseline NIHSS of 8-14, and mRS of 0-2 in patients with baseline NIHSS of 15-22. These cutpoints, based on categorizing the study population by severity of stroke, were modeled after the cutpoints used in the reanalysis of the NINDS tPA stroke trials data and the ABEST-II trial.^{3,4}

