6. RANDOMIZATION

A web-based central randomization system will be developed by the SDMC and installed on the WebDCU™ SHINE study website using a combination of covariate balance and response-adaptive randomization (RAR) method.⁶ The randomization design is aimed to preserve the randomness of treatment assignment, prevent serious imbalance in important baseline prognostic variables and promote subject recruitment while preserving the statistical test power. In summary, the probability of treatment assignment under the proposed scheme will be based on the prevention of serious imbalance in the pre-specified prognostic variables and the favorable outcome rate of each treatment arm. The specific prognostic variables at the time of randomization are: baseline NIHSS strata (3-7; 8-14; 15-22); use of IV thrombolysis (Y/N); and, site. Favorable outcome will be based on the baseline severity adjusted dichotomized mRS as previously described.

The SHINE Randomization algorithm will be fully detailed and documented in the SHINE Randomization Plan and Validation Documents. These documents will be developed prior to the enrollment initiation and stored in a secure location at the SDMC. The documents will be archived with the study database at the end of the trial. In summary, the trial will start with a 1:1

allocation scheme focusing on covariate balance. The RAR will be implemented once an adequate amount of primary outcome information is collected. With RAR, each enrolling subject will have a higher probability (greater than 50% chance) of being assigned to the treatment arm with the higher success rate based on previous subjects' responses. The SDMC's computer system will run both the 1:1 allocation and the RAR. Participating sites and members of the study team will not notice any difference between the randomization schemes and sites will only need to press one randomization button on the computer screen to obtain the assigned treatment during the course of the study. To ensure proper randomization, the unblinded statistical programmer will have access to the randomization information in order to oversee the quality control of the computer program.

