11.2 Analysis of Safety Outcomes

All adverse events and serious adverse events will be summarized by AE code in terms of frequency of the event, number of subjects having the event, severity, expectedness (anticipated/unanticipated) and relatedness to the study treatment. Clinically important adverse events including neurological worsening lasting greater than 24hours and associated with glucose concentration of < 55mg/dL and severe hypoglycemia (glucose <40 mg/dL) will be summarized. The proportion of subjects experiencing each of these events will be provided by treatment arm with two-sided 95% confidence intervals and unadjusted relative risks will be provided.

In addition to the continual monitoring of adverse events by the safety monitor and DSMB and the planned statistical monitoring for safety (described above), final analyses of specified safety outcomes will be conducted. The proportion of subjects experiencing severe hypoglycemia during the treatment period will be compared between the two treatment arms using Fisher's exact test. For the 90-day death outcome, the log-rank test will be used to compare survival curves between the two treatment arms. Providing the assumption of proportional hazards is valid, a Cox proportional hazards model will be used to analyze time to death within 90 days from randomization adjusting for use of thrombolysis treatment, baseline NIHSS score and age. All tests for safety will use a two-tailed significance level of 0.05.

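### The primary model adjusts for baseline NIHSS only as three bands; keeping the bands and adding the score within band would give a small precision gain from data already collected

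*SAP*

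**What the plan says.** SAP 10.1.2 compares the arms on favorable outcome "after controlling for the variables included in the randomization scheme". The GENMOD model has treatment as the factor of interest, with "baseline NIHSS strata (3-7, 8-14, 15-22) and thrombolysis use (Yes/No; includes both IV and IA therapies) as covariates". The test is a Wald test: a "chi-square test will be performed to compare the treatment group proportions using a two-tailed significance level of 0.05". On reporting, the SAP says: "Adjusted relative risks will be reported with two-sided 95% confidence intervals". It states neither the link nor the distribution.

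SAP 6 gives the randomization variables as "baseline NIHSS strata (3-7; 8-14; 15-22); use of IV thrombolysis (Y/N); and, site". SAP 3.1 moves the success cut at the same band edges: mRS 0 for NIHSS 3-7, then "mRS of 0-1 in patients with baseline NIHSS of 8-14, and mRS of 0-2 in patients with baseline NIHSS of 15-22".

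Protocol 8.1.4 has the NIHSS scored before randomization by a certified investigator, so the score is available for every patient. For covariates in secondary analyses of the primary outcome, SAP 10.1.2 says: "Specific covariates include age, gender, race, ethnicity, admission blood glucose, previous stroke, lacunar subtype, and time between stroke onset and treatment". The NIHSS score is not in that list. The imputation model in SAP 8 includes baseline NIHSS without saying whether as score or bands.

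**The concern.** The success cut is constant inside a band while severity is not. Patients with NIHSS 8 and 14 must both reach mRS 0-1, and patients with NIHSS 15 and 22 must both reach mRS 0-2. If prognosis worsens with the score inside a band, the band-only model leaves that variation in the residual, and the treatment estimate is a little less precise than the collected data allow. Randomization balances the bands, not the scores within them.

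Only precision is at stake. Chance imbalance within bands is already reflected in the standard error, so correcting it is the same gain described another way and should not be counted twice.

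**Working it through.** **1. The plan's own figure.** Inputs from SAP 4.1 and 10.1.2: 25% versus 32%, two-sided 0.05, 80% power. The calculation assumes 1:1 allocation.

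n per arm = [1.960·√(2·0.285·0.715) + 0.842·√(0.25·0.75 + 0.32·0.68)]² / 0.07² = 651.6, so 652 per arm, or 1304 in total. The SAP states 1314, which is within 1%. At 657 per arm the power is 80.3%. Inflation: 1314/0.97 = 1355 and 1314/0.97² = 1397, the latter close to 1400. In the SAP's sequential design (looks at 500, 700, 900, 1100 and 1400, with its stated bounds) power at 1400 is 80.8%. The stated power therefore holds with no credit for covariate adjustment.

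**2. Formula for the gain.** Let R² be the share of within-band outcome variance explained by the score. Adding the score raises effective information by about g = R²/(1 − R²). For a modest slope, R² ≈ [ln(OR)]² · V · p(1 − p). Here OR is the odds ratio per NIHSS point, V the average within-band variance of the score, and p the overall success rate.

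**3. Inputs for the gain.** From the documents, p = (0.25 + 0.32)/2 = 0.285, so p(1 − p) = 0.2038. The rest is assumed: band shares 40/35/25%, scores uniform within band, equal success rates across bands. For k equally likely scores the variance is (k² − 1)/12. That gives 2, 4 and 5.25 for bands of 5, 7 and 8 scores, and V = 0.40·2 + 0.35·4 + 0.25·5.25 = 3.51.

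**4. Hand calculation.**
- OR 0.90: R² = 0.1054²·3.51·0.2038 = 0.0079; g = 0.8%
- OR 0.82: R² = 0.1985²·3.51·0.2038 = 0.028; g = 2.9%
- OR 0.74: R² = 0.3011²·3.51·0.2038 = 0.065; g = 6.9% (the approximation runs high at this slope; without it, R² = 0.059 and g = 6.3%)

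**5. Simulation.** 1500 paired trials per scenario, N = 1314, 25% versus 32%. Bands only was compared with bands plus linear score, under a logit link and under a log link with robust standard errors. The two links agreed closely.

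| Assumed OR per point | Gain in information | Equivalent patients, 1314·(1 − 1/(1+g)) |
|---|---|---|
| 1.00 | 0% | 0 |
| 0.90 | 0.7-0.9% | 9-12 |
| 0.82 | 2.0-3.5% | 26-44 |
| 0.74 | 5.6-5.8% | 70-72 |

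The range at 0.82 covers several assumed NIHSS distributions and band-specific success rates. Calculations without simulation noise give 0.7-0.8%, 2.5-2.9% and 5.6-6.5% at the three slopes.

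**6. Power in the sequential design at N = 1400.** From 80.8%: 81.2% with 1% more information, 81.9% with 3%, and 82.8% with 5%.

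**7. Score instead of bands.** Replacing the bands by the score alone changed information by −1.3% to +1.6% relative to bands only. That is not a dependable gain.

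**The case against.** The strongest defense is that the bands are deliberate. They are randomization strata, and they define the endpoint, so the chance of success can jump between NIHSS 7 and 8 and between 14 and 15. A single line through the score cannot follow those jumps. This stands, and it is why the bands must stay. A reader might infer that the plan discards precision for no reason, or that the score should replace the bands; SAP 3.1 and 6 and step 7 above do not support either. The defense does not rule out an added covariate. The model already departs from the randomization scheme, since it omits site and counts IA as well as IV thrombolysis.

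A reader might also see an inconsistency with SAP 11.2, where the Cox model for death is fitted "adjusting for use of thrombolysis treatment, baseline NIHSS score and age". Death has no severity-dependent cut, so coding NIHSS differently there is not a contradiction. It shows only that the score is available for adjustment.

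Nor do the documents show that most of the remaining severity information lies within bands. They give no success rate by band, no NIHSS distribution and no within-band slope. An odds ratio of 0.74 per point would put the odds of success at NIHSS 22 at 0.74⁷ = 12% of those at NIHSS 15, and nothing in the documents supports so steep a slope.

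Finally, Protocol 12.1 takes no credit for regression and calls its sample size conservative, so the trial is not underpowered for want of this term. That also stands.

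**Conclusion.** This is an optional refinement, not an error. The primary model ignores within-band severity, and no covariate list for an analysis of the primary outcome names the score. Under the assumed slopes, adding it to the bands is worth between nothing and about 6% more information, or roughly 0-2 points of power. The top of that range needs a steep slope; at an odds ratio of 0.90 per point the gain is under 1%. Slope, NIHSS distribution and band-specific rates are all assumptions, and 1:1 allocation was used although SAP 6 later moves to response-adaptive allocation. Type I error, validity and the stated 80% power do not depend on the change.

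**What to change.** Before the first unblinded look, amend SAP 10.1.2 to keep the three strata and thrombolysis and add baseline NIHSS score as one linear term centered within stratum (for example at the band midpoints 5, 11 and 18.5). Use the same model at every interim analysis. State the link and the fitting method. A log link with robust standard errors gives relative risks directly and showed nearly the same gain as a logit model; a log-binomial fit with a continuous covariate may fail to converge and would need a named fallback. State in SAP 8 that the imputation model carries the score as well as the strata, so that it matches the analysis model.

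If the sponsor prefers to leave the primary model alone, prespecify this one as a sensitivity analysis. The cost is one extra parameter and a few more words of model specification. No new data are needed and the sample size does not change.

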4. SAMPLE SIZE DETERMINATION FOR THE PRIMARY EFFICACY OBJECTIVE

4.1 Sample Size Estimation

The primary outcome variable is the overall proportion of subjects experiencing a favorable outcome 90-days post randomization, where favorable is defined by the dichotomized mRS score as adjusted to the baseline NIHSS (stroke severity). Our preliminary data suggest a 25% rate of favorable outcome in the control group at 90 days is reasonable. A clinically relevant absolute difference in success rates between the two interventions is chosen as 7% (success rate_{control}=25%; success rate_{infusion}=32%). If the IV insulin group does not have at least a 7% or higher success rate than the control group, then IV insulin within 12 hours of symptom onset will not be considered a worthwhile therapy for hyperglycemic acute ischemic stroke patients.

Based on the above information and taking into consideration four planned interim analyses (see Section 10.1.4 for details), the study is powered to assure 80% likelihood of identifying a difference in success rates greater than or equal to 7%. Sample size estimation is based on the comparison of independent proportions adjusting for baseline NIHSS. The maximum sample size required for randomization is 1314 subjects (657/treatment group). Although every attempt will be made to avoid drop outs and losses to follow up, the required sample size is inflated for a 3% non-adherence rate. The total number of patients required for randomization is 1400.

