8. MISSING DATA

Under the ITT principle, all subjects who are randomized are included in the analysis. Although every attempt will be made to prevent incomplete data, a certain amount of missing data is inevitable due to losses to follow up or withdrawn consents. The investigators also need to consider primary outcome data that is collected late (i.e., past the pre-specified data entry timelines of +/-14 days). Based on discussions with the SHINE Executive Committee and clinical expertise, primary outcome data (i.e., 90-day mRS) collected past the data entry timelines will only be used for the primary analysis if the collection falls within -14 days/+30 days from the scheduled date. Data collected outside the 30-day window (only allowed up to 180 days to collect data) will be considered missing for the primary outcome.

A thorough analysis of variables, reasons and patterns of missing data will be conducted. Based on other large acute stroke trials that capture 90-day mRS, we anticipate no more than a 3% lost to follow up rate. At the time of each planned analysis (interim and final), the unblinded statistician will report the amount of missing primary outcome data. Multiple imputation using SAS PROC MI and MIANALYZE will be used to impute the missing 90-day mRS outcome data. In summary, 5 imputed data sets will be generated using PROC MI. The imputation model will include the primary analysis variables (90-day mRS, treatment, baseline NIHSS, thrombolysis use) plus age, gender and 6-week mRS. Each imputed data set will be analyzed according to the specified primary analysis (Section 10.1.2) and MIANALYZE will be used to combine the

results from the multiple imputed data sets to obtain a single set of parameter estimates. The multiple imputation method assumes missing at random (MAR) which means that the probability of missing outcome data can depend on the observed values of the individual but not on the missing values of the individual. Although we anticipate minimal missing data, sensitivity analyses will be conducted to assess the impact of any bias due to missing data. The primary analysis will be re-run using the following methods:

- Complete case analysis (only those with 90-day outcome)
- Worst case analysis (assume any subject with missing 90 day outcome to be considered a 'failure')
- Inclusion of primary outcome data collected outside the defined window

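### The primary model omits age, a baseline covariate the SAP uses elsewhere; adding it would probably gain a little power without extra patients

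*SAP*

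**What the plan says.** SAP section 10.1.2 compares the arms on favorable 90-day outcome in a generalized linear model. Treatment is the factor of interest, with "baseline NIHSS strata (3-7, 8-14, 15-22) and thrombolysis use (Yes/No; includes both IV and IA therapies) as covariates". The test is a Wald test: a "chi-square test will be performed to compare the treatment group proportions using a two-tailed significance level of 0.05". Adjusted relative risks are to be reported, but no link function is named. The stated reason for the covariate set, here and in protocol section 12.2.3, is that these are the randomization variables.

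Age appears in three other places:

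- The imputation model for the 90-day mRS (SAP section 8) contains the primary-model variables, ending "thrombolysis use) plus age, gender and 6-week mRS".
- The Cox model for 90-day death (SAP section 11.2) is fitted "adjusting for use of thrombolysis treatment, baseline NIHSS score and age".
- SAP section 10.1.2 and protocol section 12.2.3 list age among the covariates for secondary adjusted analyses of the primary outcome.

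SAP section 4.1 states that "the study is powered to assure 80% likelihood of identifying a difference in success rates greater than or equal to 7" percent, with 25% favorable in the control group and 32% in the infusion group. It mentions adjustment for baseline NIHSS but not for age.

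**The concern.** A baseline covariate that predicts the outcome within NIHSS strata makes the treatment comparison more precise when it is in the model, at no cost in recruitment. The SAP uses age for this endpoint's imputation and for its secondary adjusted analyses, yet the confirmatory test does without it. Age is not a randomization factor either (SAP section 6), so the design does nothing to limit a chance imbalance in age.

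Two things are at stake. One is some power. The other is clarity: if the age-adjusted and primary analyses fell on opposite sides of the final boundary (Z = 2.02, SAP section 10.1.3), the model without age would decide, and the better-adjusted result would count only as secondary.

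**Working it through.** **Inputs from the documents.** Rates 25% and 32%; two-sided 0.05; 80% power; 1314 patients (657 per arm) before inflation and 1400 after; looks at 500, 700, 900, 1100 and 1400; efficacy boundaries 2.97, 2.86, 2.65, 2.42, 2.02; futility boundaries 0.06, 0.13, 0.45, 1.05, 2.02.

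**Step 1: reproduce the plan's figures.** With mean rate 0.285, the pooled two-proportion formula gives

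n per arm = [1.96·√(2·0.285·0.715) + 0.842·√(0.25·0.75 + 0.32·0.68)]² / 0.07² = (1.251 + 0.536)² / 0.0049 ≈ 652,

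or 1304 in total against the stated 1314. At 657 per arm the power is 80.3%. For the inflation, 1314/0.97 = 1355 and 1314/0.97² = 1397, which rounds to 1400.

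A simulation of 400,000 trials with the SAP boundaries at 1400 patients rejects in 81.0% of trials under the alternative and 4.8% under the null. Its stopping probabilities under the alternative are 0.12, 0.13, 0.19, 0.22 and 0.34. All of these match SAP section 10.1.3 and Appendix A. The plan therefore reaches its stated power without age.

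**Step 2: add age.** The documents give no age effect, so it is assumed over a range. Let R² be the share of outcome variance that age explains. Adjusting for age acts roughly like dividing the sample size by (1 − R²):

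power = Φ{[0.07·√(n/(1 − R²)) − 1.251] / 0.636}, with n = 657.

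- R² = 0: (0.07·25.63 − 1.251)/0.636 = 0.853, power 80.3%.
- R² = 0.007: n becomes 661.6, power 80.6%.
- R² = 0.085: n becomes 718, power 83.7%.

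The primary model was then simulated with and without age (log-link Poisson, robust variance, N = 1314, 6,000 trials per row). Odds ratios are for favorable outcome per SD of older age. The last column is the share of trials with at least one fitted risk of 1 or more when age enters linearly. The five-look column applies the SAP boundaries to an effective sample of 1400/(1 − R²). Patients' worth is 1314·R².

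| OR per SD | R² | Simulated, without → with age | Formula, with age | Five looks at 1400, with age | Patients' worth | Fitted risk ≥ 1 |
|---|---|---|---|---|---|---|
| 1.00 | 0 | 80.3 → 80.3% | 80.3% | 81.0% | 0 | 0% |
| 0.83 | 0.7% | 79.9 → 80.4% | 80.6% | 81.2% | 9 | 0% |
| 0.74 | 1.8% | 80.2 → 80.9% | 81.0% | 81.7% | 23 | 0.3% |
| 0.67 | 3.2% | 80.2 → 81.5% | 81.6% | 82.2% | 42 | 5% |
| 0.57 | 5.8% | 80.2 → 82.6% | 82.6% | 83.3% | 76 | 44% |
| 0.50 | 8.5% | 80.2 → 83.6% | 83.7% | 84.3% | 111 | 87% |

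The Monte Carlo standard error of one simulated power is √(0.8·0.2/6000) ≈ 0.5 points. The with/without difference is paired and more precise. Two further fixed-sample simulations at N = 1400, with 6,000 and 8,000 trials, gave gains of 0.3 and 0.4 points at OR 0.8, 0.7 and 0.8 at OR 0.7, 1.4 and 1.5 at OR 0.6, and 2.7 and 3.4 at OR 0.5.

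**Step 3: type I error.** With both arms at 25% (4,000 trials each), the model with age rejected in 4.95%, 5.0% and 4.9% of trials when the age odds ratio was 1.0, 0.67 and 0.50.

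**The case against.** The strongest reply is that this is a declared design choice: adjust for the randomization variables, and treat age-adjusted analyses as secondary. That is legitimate, and nothing in it is invalid or contradictory. The rule is not strictly followed, though. SAP section 6 lists NIHSS strata, IV thrombolysis and site; the model drops site and widens thrombolysis to include IA therapy. The rule alone therefore does not explain leaving age out.

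The second reply is that using age elsewhere does not show it is prognostic for this endpoint. This stands. The imputation model also holds the 6-week mRS, a post-randomization variable that could not enter the primary model, and death is a different outcome. The size of the gain is therefore an assumption.

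The third reply is that there is no shortfall to repair. This also stands: the target is 80% and the design gives 81%.

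A reader might also set the gain against the extra patients in the re-estimation table of SAP section 4.2 and infer that the plan pays heavily for similar amounts of power. The documents do not support this. The table runs to 228 extra patients, and its increases apply to overall event rates above the design value of 0.285. The same section reserves an increase for observed rates of 0.31 or more, with DSMB notification only at 150 or more extra subjects. At 0.325, where power is 78% and 108 more patients are indicated, no notification would follow. The plan thus tolerates losses of about this size.

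**Conclusion.** The point holds as a modest missed efficiency. For odds ratios of 0.8 to 0.5 per SD of age, adding age would raise power by roughly 0.3 to 3.5 points. The gain is about zero if age is not prognostic within NIHSS strata. Type I error stays near 5% and no patients are added.

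Three stronger readings are not supported: that the trial is underpowered without age, that the omission biases the treatment effect, and that the change is free. On the last, linear age under a log link often produces fitted risks of 1 or more at the odds ratios where the gain is largest, so the estimator has to be chosen in advance.

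The figures rest on assumptions that are not in the documents: NIHSS strata of 40/35/25%, thrombolysis in 50%, equal favorable rates across strata, age normally distributed and linear on the logit scale, and 1:1 allocation. Response-adaptive randomization was not modelled.

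**What to change.** Before any unblinded look, amend SAP section 10.1.2 so that continuous age joins NIHSS strata and thrombolysis in the primary model, for interim and final tests alike. State the functional form of age, and state that the model uses a log link fitted by Poisson regression with robust variance, so that the adjusted relative risk remains estimable where a log-binomial fit might fail. Keep the model without age as a prespecified sensitivity analysis.

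The cost is a short SAP amendment and the matching programming for five analyses. No data collection changes, and the imputation model in SAP section 8 already includes age. If an unblinded look has already taken place, leave the primary model alone and report the age-adjusted analysis as the secondary analysis already planned.
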